9.4.2 Primary Endpoint(s)

The primary endpoint is the change from baseline in the modified UMSARS score measured at the Week 48 visit. The items in the modified UMSARS will contain the following Part I items: Speech, Cutting Food and Handling Utensils, Dressing, Hygiene, Walking and Urinary Function. The following Part II items will also be included: Arising from Chair, Posture, and Gait. In the analysis of all items, the response categories of 0 and 1 will be combined into a single category before summing the individual items to derive the modified UMSARS.

The primary estimand, for the primary endpoint, will pursue a hypothetical strategy of estimating the effect of BHV-3241 relative to placebo had all subjects stayed on treatment. Using the mITT population, the summary will be the difference between placebo and BHV-3241 treated subjects at the Week 48 visit. The summary will be computed using a Mixed Model for Repeated Measures (MMRM) that will include fixed effect factors for treatment group, randomization strata (MSA-C or MSA-P, Possible or Probable MSA diagnosis, and country), visit, and the treatment group by visit interaction. Baseline modified UMSARS score will enter the model as a covariate, and subject will be a random effect. Intercurrent events that lead to discontinuation, or lack of data, will be handled by only using the-on treatment data. MMRM-based estimates (i.e., least-squares mean [LSM] with corresponding SD and 95% CI) of values and changes from baseline will be presented by treatment group and week. In addition, the LSM difference in change from baseline between treatment groups (BHV-3241 – placebo) at Week 48 with corresponding SD, 95% CI, and p-value from MMRM will also be presented. Since the estimate is calculated using a likelihood-based approach, the analysis is based on a Missing at Random (MAR) assumption. Sensitivity analyses will include multiple imputation of missing data using a copy increment from reference method.

Observed values and changes from baseline in the modified UMSARS scores will also be summarized using descriptive statistics over time by treatment group during the Randomization Phase.

Details of these analyses are provided in the SAP.

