4 ANALYSIS SETS, TREATMENT GROUPS, AND SUBGROUPS

4.1 Analysis Sets

The following populations will be evaluated and used for presentation and analysis of the data:

- Enrolled subjects: Subjects who signed an informed consent form and were assigned a Patient Identification number (PID).
- Randomized subjects: Enrolled subjects who received a treatment assignment from the IWRS.
- Treated/Safety: Enrolled subjects who received at least 1 dose of blinded study therapy (Verdiperstat or placebo).
- Modified Intent-to-Treat (mITT) subjects: Randomized subjects who received at least one dose of blinded study therapy and provided a baseline and at least one post-baseline efficacy assessment.
- Open-Label Extension Treated subjects: Enrolled subjects in the extension phase who received at least 1 dose of open-label study therapy (Verdiperstat).
- Verdiperstat Treated Participants: Enrolled subjects who received at least 1 dose of Verdiperstat (blinded or open-label)

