6.1.3 Handling of Missing Data

Unless otherwise noted, efficacy analyses will be based on observed data only. For the principal analysis of efficacy for primary, secondary and endpoints, no imputation will be performed on missing data following discontinuation from the study.

If the primary and secondary endpoints results are found to be statistically significant, then sensitivity analyses using multiple imputation (MI) will be conducted on the primary and key secondary endpoints using the copy increment from reference and jump to reference methods to assess the impact of the missing at random (MAR) assumption (see Section 6.3.2.3).

For efficacy analyses, partial or missing dates will not be imputed. The relative study days, where determined, will be calculated for full dates only.

If the start date of an AE is partially or completely missing, the date will be compared as far as possible with the date of the start of administration of study drug. The AE will be assumed to be treatment-emergent if it cannot be definitively shown that the AE did not occur or worsen during the treatment-emergent period (worst case approach).

The following general rules will be used:

• If the start day is missing but the start month and year are complete, an AE will only be excluded as being treatment-emergent if the start month/year is before the month/year of study drug administration or if the stop date is before study drug administration.

- If the start day and month are missing but the start year is complete, an AE will only be excluded as being treatment-emergent if start year is before the year of study drug administration or if the stop date is before study drug administration.
- If the start date is completely missing, an AE will be considered treatment-emergent unless the stop date is before study drug administration.

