6.1.4 Adjustments for Covariates and Stratification

The randomization was stratified by disease subtype (MSA-P vs. MSA-C), diagnostic category (possible MSA vs. probable MSA), and country. Hence, treatment group comparisons of continuous efficacy endpoints will be adjusted by disease subtype, diagnostic category, and country. If there are sparse data within a stratum, then stratum may be combined.

The analysis of the primary endpoint and other continuous efficacy endpoints will also be adjusted by the baseline value of the endpoint as a covariate in statistical models.

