6.3.1 Continuous Efficacy Endpoints

Measurements are slotted into analysis visits as described in Section 7.2.

Descriptive Analyses

Summary statistics for parameter values are tabulated at select time points by treatment group during the DB and OLE phases, separately.

Treatment Group Comparison Using MMRM

Treatment groups are compared and assessed using MMRM with the following variables:

- Dependent variable, e.g., modified UMSARS score
- Fixed effects (categorical variables): treatment group, visit, treatment group-by-visit interaction, randomization strata (i.e., disease subtype, diagnostic category, and country). Visit represents on-study analysis visit.
- Covariate (continuous variable): baseline value of dependent variable, baseline neurofilament level
- Random effect: subject

Error degrees of freedom are determined by the Kenward-Roger approximation.

The covariance structure for within subject error will be initially modeled using the unstructured covariance matrix. If the model fails to converge, then a Huynh-Feldt structure will be used, followed by an AR(1) structure.

The following statistics are tabulated from the MMRM at select analysis visits:

- Least-squares mean with standard error (SE) and 95% CI by treatment group
- Difference in least-squares means between treatment groups (Verdiperstat placebo) with df, SE, 95% CI, and p-value.

Treatment Group Comparison Using ANOVA

Treatment groups are compared and assessed using ANOVA with the following variables:

- Dependent variable, e.g., brain volume
- Fixed effects (categorical variables): treatment group, baseline value of the dependent variable, randomization strata (i.e., disease subtype, diagnostic category, and country)

The following statistics are tabulated from the ANOVA results:

- Least-squares mean with standard error (SE) and 95% CI by treatment group
- Difference in least-squares means between treatment groups (Verdiperstat placebo) with df, SE, 95% CI, and p-value.

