and concurrent treatments. Study dropout including dropouts and missed visits due to COVID-19 pandemic (and corresponding discontinuation of assessments) will be handled by a hypothetical strategy to estimate what the outcome would have been at the designated time point if all subjects were continued to be assessed.

d. The mean change from baseline between treatment and placebo on the primary endpoint will be compared at 48 weeks. A significant difference with an error rate of 5% will be required for success.

The summary will be computed using a Mixed Model for Repeated Measures (MMRM) that will include fixed effect factors for treatment group, randomization strata (i.e., disease subtype, diagnostic category, and country), visit, and the treatment group by visit interaction. Baseline modified UMSARS score and the baseline neurofilament level will enter the model as covariates, and subject will be a random effect. Repeated measurements are made on each subject. The covariance structure for within subject error ("R" matrix in SAS proc mixed) will be initially specified as unstructured. If the model fails to converge, then a Huynh-Feldt structure may be used, followed by an AR(1) structure. Error degrees of freedom will be calculated using Kenward-Roger approximation if an unstructured covariance structure fits appropriately; otherwise, a sandwich estimator will be utilized to estimate the covariance structure and degrees of freedom will be calculated using the between-within method.

MMRM-based estimates (i.e., least-squares mean [LSM] with corresponding SD and 95% CI) of values and changes from baseline will be presented by treatment group and week. In addition, the LSM difference in change from baseline between treatment groups (Verdiperstat – placebo) at Week 48 with corresponding SD, 95% CI, and p-value from MMRM will be presented.

Observed values and changes from baseline in the modified UMSARS score will be summarized using descriptive statistics over time by treatment group.

Effect sizes (Cohen's D) of the individual items within the modified UMSARS will also be summarized to assess the strength of the effect of Verdiperstat on each individual item.

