For each analysis, the imputed data will consist of 1000 imputed data sets (using a MCMC length of 100). Both the parameter-estimation model and the imputation model will include fixed effect factors for treatment group, visit, and the treatment group by visit interaction. The baseline modified UMSARS score and visit by baseline interaction terms will be entered as covariates.

For each imputed dataset, the change from baseline for the modified UMSARS score at Week 48 will be based on observed and imputed data. An ANCOVA model will be used with baseline

modified UMSARS score and randomization strata (i.e., disease subtype, diagnostic category, and country) as covariates, and treatment groups will be compared at Week 48 based on LSM difference between Verdiperstat and placebo in each of the imputed data sets. Results from the analysis of each imputed dataset (LSM treatment differences and standard errors [SE]), will be combined using Rubin's imputation rules to produce a pooled LSM estimate of treatment difference, 95% CI, and a pooled p-value for the test of null hypothesis of no treatment effect.

An additional sensitivity analysis will be conducted on the primary endpoint using the same main analysis described in Section 6.3.2.1 but with a narrower visit window for Week 48 (See Section 7.2).

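### The SAP adds baseline neurofilament to the primary MMRM without noting the departure from the protocol, and no visible rule keeps mITT subjects who lack a value in the test

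*SAP*

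**What the plan says.** The protocol's primary MMRM (9.4.2) has treatment, the randomization strata, visit and treatment by visit, with one continuous covariate: "Baseline modified UMSARS score will enter the model as a covariate, and subject will be a random effect".

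The SAP's general MMRM (6.3.1) lists as continuous covariates "baseline value of dependent variable, baseline neurofilament level", and its primary analysis section (6.3.2.1) agrees: "Baseline modified UMSARS score and the baseline neurofilament level will enter the model as covariates".

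Other parts of the SAP do not mention neurofilament:
- 6.1.4, on covariate adjustment, names the strata and says that continuous endpoints "will also be adjusted by the baseline value of the endpoint as a covariate in statistical models".
- The supplementary ANCOVA in 6.3.2.2 uses the strata and the baseline modified UMSARS score.
- In 6.3.2.3 the parameter-estimation and imputation models use treatment, visit, their interaction, baseline score and baseline by visit. The final step ("An ANCOVA model will be used with baseline" score) adds the strata.

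The analysis set is mITT. Beyond randomization and a dose, it asks only that a subject "provided a baseline and at least one post-baseline efficacy assessment" (SAP 4.1). On missing data, SAP 6.1.3 says "Unless otherwise noted, efficacy analyses will be based on observed data only". The software reference in 6.3.2.1 is to the R "matrix in SAS proc mixed".

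**The concern.** A mixed model fitted in that procedure omits every record with a missing covariate. Baseline neurofilament is one value per subject, so a subject without it contributes nothing at any visit, even with a complete set of UMSARS scores. The likelihood-based missing-at-random argument covers missing outcomes, not missing covariates. The confirmatory test would then run on an unnamed subset of mITT while being reported as an mITT analysis.

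Three further things are at stake. The SAP states that it is based on protocol version 7.0, yet its confirmatory model differs from that protocol's model with no visible explanation. The MSA-QoL motor, MSA-QoL non-motor and UMSARS Part I and II analyses point to 6.3.1 and so inherit the same deletion. And the imputation analyses, meant to probe the missing-data assumption, omit the covariate. They may therefore keep subjects that the main model drops, and a gap between the two could come from the model, the subjects or the assumption.

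**Working it through.** **Where neurofilament appears**

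| Place | Baseline terms | Neurofilament |
|---|---|---|
| Protocol 9.4.2, primary MMRM | score, strata | no |
| SAP 6.1.4, covariates | baseline value, strata | not named |
| SAP 6.3.1, general MMRM | baseline value, strata | yes |
| SAP 6.3.2.1, primary MMRM | score, strata | yes |
| SAP 6.3.2.2, supplementary ANCOVA | score, strata | no |
| SAP 6.3.2.3, imputation models | score, score by visit; no strata | no |
| SAP 6.3.2.3, final ANCOVA | score, strata | no |
| SAP 6.3.3.1, CGI-I | baseline CGI-S named as the covariate | unclear |

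**Is there a rule for a missing value?** The visible missing-data text (SAP 3.2, 6.1.3, 6.3.2.3) deals with scale items, outcomes after discontinuation, intermittent missing outcomes and dates. It says nothing about a baseline covariate.

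**The plan's own figure.** Inputs from protocol 9.2 and SAP 5.1: placebo change 4.88, SD 4.85, 40% improvement, 130 evaluable per group, about 20% dropout. Two-sided alpha is 0.05 (protocol 9.4.5, SAP 5.2).
- Difference: 0.40 × 4.88 = 1.952.
- Standardised difference: 1.952 / 4.85 = 0.402.
- Noncentrality: 0.4025 × √(130/2) = 3.245, so t-test power is 89.8%. The stated 90% is reproduced.
- Randomized: 260 / 0.80 = 325, as stated.

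**Effect of deletion.** Let m be the share of otherwise evaluable subjects without a value, and r the partial correlation of neurofilament with the outcome. The documents give neither, so both are assumptions. Then n per group = 130(1 − m), residual SD = 4.85√(1 − r²), and noncentrality = (1.952 / residual SD) × √(n/2). At r = 0.25 the residual SD is 4.85 × √0.9375 = 4.696.

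| m | evaluable | noncentrality, r = 0 | power, r = 0 | noncentrality, r = 0.25 | power, r = 0.25 |
|---|---|---|---|---|---|
| 5% | 247 | 3.163 | 88.3% | 3.266 | 90.2% |
| 10% | 234 | 3.078 | 86.6% | 3.179 | 88.6% |
| 15% | 221 | 2.992 | 84.6% | 3.090 | 86.8% |

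The reference is 89.8%: nobody deleted and no covariate. Deletion and adjustment cancel when (1 − m)/(1 − r²) = 1, that is m = r². At r = 0.25 that is 0.0625, about 6% missing. At 10% missing, r would have to be √0.10 = 0.32.

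**The case against.** The strongest reply is that the SAP is the governing document on analysis detail. The protocol defers details to it, and the two SAP sections that actually specify the MMRM agree. Section 6.1.4 is general and does not say that nothing else enters. This stands: a reader might infer that the confirmatory p-value is open to choice between two models, but within the SAP one model is specified. What remains is an undocumented departure from the protocol and an incomplete covariate section.

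Second, a prognostic covariate pays for some of the subjects it loses. This also stands. A reader might infer a demonstrated power loss from the r = 0 column. At r = 0.25 and 5% missing, however, power is slightly above the reference.

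Third, biomarker text is redacted in both documents, so a collection or handling rule could sit there. That cannot be excluded. But the readable sections 6.1.3, 6.1.4 and 6.3.2.1, where such a rule belongs, neither state one nor refer to one.

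Four other stronger readings are not supported:
- *All four key secondary tests lose subjects.* CGI-I names baseline CGI-S as the covariate, and whether neurofilament remains in that model is unclear.
- *The value enters untransformed.* The SAP says only level; its scale is not stated in the visible text.
- *The loss would be large because CSF collection is optional.* The visible text does not say whether the value comes from blood or CSF.
- *The treatment estimate is biased.* A baseline value missing before dosing is not affected by treatment, so the issue is precision and the labelling of the population.

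**Conclusion.** The point holds in this form. The SAP's primary MMRM contains a covariate that the protocol model, SAP 6.1.4, the supplementary ANCOVA and the imputation models lack. With no visible rule for a missing value, following the plan as written would analyse a subset of mITT in the primary test and in three of the four key secondary tests.

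The size is unknown, because neither the missing rate nor the prognostic strength of neurofilament is given. Over an assumed 5% to 15% missing, power lies between 84.6% and 88.3% if the covariate is uninformative, and between about 86.8% and 90.2% at a partial correlation of 0.25, against 89.8% at the design stage. These figures use the plan's two-sample t-test approximation, not the MMRM itself. They also assume that missing values are spread equally over the arms.

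It should be corrected because the confirmatory model and the subjects in it ought to be unambiguous before unblinding. Neither bias nor a raised type I error is shown.

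**What to change.** Amend the SAP before unblinding:
1. Keep baseline neurofilament in the primary model. Replace a missing baseline value by the mean over all subjects with a value, computed without reference to treatment arm, so that every mITT subject stays in the test.
2. Use the same baseline covariates and strata in 6.1.4, 6.3.1, 6.3.2.1, the supplementary ANCOVA of 6.3.2.2, and both the imputation and analysis models of 6.3.2.3. The imputation models need the strata as well as neurofilament; adding neurofilament alone would not align them. They would still differ from the main analysis in the baseline-by-visit term and in their declared estimand.
3. State in 6.3.3.1 whether the CGI-I model includes neurofilament.
4. State that this model supersedes the one in protocol 9.4.2.

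The cost is SAP wording and one derived variable. The downside is single-value imputation of a baseline covariate. That is harmless under randomization, because the filled value does not depend on arm; it only means that those subjects gain nothing from the adjustment. A log scale for neurofilament would be a matter of preference and is not part of this correction.

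### The MMRMs pair a random subject effect with an unstructured (then Huynh-Feldt) R matrix, so the subject variance is not identifiable and the redundant term can itself set off the convergence fallback

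*SAP*

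**What the plan says.** **SAP 6.3.2.1 (primary endpoint).** After the fixed effects and baseline covariates, the text says "subject will be a random effect. Repeated measurements are made on each subject". It then turns to the within-subject error matrix, which it identifies as the R matrix of SAS PROC MIXED, and says that this "will be initially specified as unstructured. If the model fails to converge, then a Huynh-Feldt structure may be used, followed by an AR(1) structure". Kenward-Roger degrees of freedom apply if the unstructured matrix fits appropriately; "otherwise, a sandwich estimator will be utilized to estimate the covariance structure and degrees of freedom will be calculated using the between-within method".

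**SAP 6.3.1 (general MMRM, used for the secondary endpoints).** The model list includes "Random effect: subject", and the next lines say: "The covariance structure for within subject error will be initially modeled using the unstructured covariance matrix". The fallback order is the same, but here Huynh-Feldt is mandatory rather than permitted. Kenward-Roger is stated without the sandwich exception.

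**Protocol 9.4.2.** "Baseline modified UMSARS score will enter the model as a covariate, and subject will be a random effect". No R structure is given there, so the protocol sentence alone contains no redundancy.

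Neither document says that the random effect is only a name for the repeated-measures unit, or that it is dropped when R is unstructured.

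**The concern.** A random subject effect and an unstructured R matrix describe the same thing twice. Because the SAP names the R matrix separately, a programmer following it literally would write both a RANDOM and a REPEATED statement.

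This matters because SAP 6.3.2.1 hangs two decisions on whether the unstructured model converges and fits: which covariance structure is used, and whether the primary test uses Kenward-Roger or the sandwich estimator with between-within degrees of freedom. The SAP does not say whether a singular Hessian or a subject variance set to zero counts as failure. A fault in the specification, rather than anything in the data, could therefore decide which analysis yields the primary p-value. The first fallback, Huynh-Feldt, has the same fault.

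**Working it through.** **The plan's own figure.** The only related number is the sample size (SAP 5.1). The difference is 0.40 × 4.88 = 1.952 points with SD 4.85. Then n per group = 2 × (1.960 + 1.282)² × 4.85² / 1.952² = 129.7, so 130 per group and 260 in total; 260 / 0.8 = 325. It reproduces, and nothing below depends on it.

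**Inputs.** Post-baseline UMSARS visits: 5 (Weeks 4, 12, 24, 36, 48; SAP 6.3.2.1). Post-baseline MSA-QoL visits in the double-blind phase: 2 (Weeks 24, 48; SAP Table 4 and 6.3.3.2).

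**Model as written.** The marginal covariance of one subject's visits is V = τ²J + R, where τ² is the subject variance and J is a matrix of ones.

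- *Unstructured R.* Every cell of R is free. For any τ², R − τ²J is another unstructured matrix giving the same V. With 5 visits there are 5 × 6 / 2 = 15 distinct cells and 15 + 1 = 16 parameters.
- *Huynh-Feldt R.* The diagonal is sᵢ² and the off-diagonal is (sᵢ² + sⱼ²)/2 − λ. Adding τ² to every cell gives diagonal sᵢ² + τ² and off-diagonal ((sᵢ² + τ²) + (sⱼ² + τ²))/2 − λ. That is Huynh-Feldt again with the same λ. Checked numerically for τ² = 0, 1, 2 and 3, the largest difference is 0.
- *AR(1) R.* With 5 visits the added constant cannot be absorbed, so the model is identifiable. With 2 visits V has only two distinct values, σ² + τ² and σ²ρ + τ², for three parameters.

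Rank of the derivative of V with respect to its parameters:

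| Visits | R structure | R alone: parameters / rank | R + subject: parameters / rank |
|---|---|---|---|
| 5 | Unstructured | 15 / 15 | 16 / 15 |
| 5 | Huynh-Feldt | 6 / 6 | 7 / 6 |
| 5 | AR(1) | 2 / 2 | 3 / 3 |
| 2 | Unstructured | 3 / 3 | 4 / 3 |
| 2 | Huynh-Feldt | 3 / 3 | 4 / 3 |
| 2 | AR(1) | 2 / 2 | 3 / 2 |

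**What a fit does.** One data set was simulated with 325 subjects, 5 visits, about 20% drop-out and Week 48 SD 4.85. The earlier SDs (2.0, 2.7, 3.5, 4.2) and a correlation of 0.85 per 12 weeks are assumptions. For unstructured plus subject, −2 REML is 3378.72334 at τ² = 0, 0.25, 0.5 and 1.0, so the likelihood is flat in τ². The Hessian has one zero eigenvalue. Without the subject effect its smallest eigenvalue is 0.095, so it is positive definite. The Week 48 difference and its standard error are −2.1324 and 0.5522 at each of the four τ² values, and τ² = 0 is unstructured alone.

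Only the split between τ² and R is unidentified. V itself, and hence the Week 48 contrast and its model-based standard error, are identified.

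**The case against.** **The wording may be loose.** Neither document names a G matrix or a RANDOM statement, and the sentence on repeated measurements follows at once. The random effect could simply mean the repeated-measures unit. That is possible, but the SAP lists it as a separate model term in two sections and does not say so.

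**If the model is fitted, nothing changes.** This stands. Software may set the subject variance to zero or issue a warning and return the unstructured answer. The documents give no basis for a probability that the fallback is reached, so the fair statement is that the redundant term can trigger it, not that it will.

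**A reader might infer that the primary standard error would be badly understated if the chain ended at AR(1) plus subject.** The SAP does not support this. In a simulation of 400 trials (162 per arm, SD rising from 1.9 to 4.85, correlation 0.85 per 12 weeks, drop-out of 18% and 15% missing at random; all but the 4.85 are essentially assumptions), the model-based standard error was 0.41 against an actual 0.56. But SAP 6.3.2.1 prescribes the sandwich estimator there, which gave 0.56 and 95% coverage (84% with the model-based value).

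**A reader might also infer a biased treatment effect.** In a 120-run simulation with similar assumptions, AR(1) plus subject gave −1.90 against a true −1.95. The gap of 0.05 is about one Monte Carlo standard error (0.54 / √120 = 0.049). Single-arm means were off by −0.25 and −0.20, but these largely cancel in the tested contrast.

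**A reader might conclude that the fallback list must be replaced.** It need not be. Huynh-Feldt already has visit-specific variances and is identifiable once the subject effect is gone. Heterogeneous Toeplitz and heterogeneous AR(1) would assume equal spacing just as AR(1) does.

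**Conclusion.** The specification is wrong as written. The first-choice structure and the first fallback are both over-parameterised by one for every MMRM endpoint. For the two MSA-QoL key secondary endpoints no listed structure is identifiable with the subject effect. For the five-visit endpoints, the first identifiable structure in the listed order is AR(1), the most restrictive.

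The rank result is algebra. It assumes only that the subject effect is fitted literally and that the visits are those in SAP Table 4. The consequence is procedural and depends on software behaviour: a singular Hessian or non-convergence that comes from the redundant term can change the covariance structure and, for the primary endpoint, remove Kenward-Roger. It is not a demonstrated bias or a wrong standard error in the primary test.

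The secondary endpoints lack one safeguard. SAP 6.3.1 does not carry the sandwich rule, so as written a fallback there would keep a model-based standard error.

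**What to change.** 1. In SAP 6.3.1 and 6.3.2.1, and for consistency in protocol 9.4.2, delete the random subject effect. State that within-subject correlation is modelled through the R matrix only (`REPEATED visit / SUBJECT=subject TYPE=UN`). All three listed structures are then identifiable with 5 and with 2 visits, and Huynh-Feldt can stay as first fallback.
2. Align SAP 6.3.1 with 6.3.2.1 on the sandwich estimator and between-within degrees of freedom when the unstructured matrix is not used, and on whether the fallback is mandatory or optional.
3. Helpful but not essential: one sentence defining what counts as failure to converge.

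The cost is wording in two SAP sections and one protocol sentence, with no effect on data, patients or sample size. It should be settled before unblinding, because it fixes which model yields the primary p-value.
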